7.2.1 Serious Adverse Events (SAEs) and Product Complaint (PC) Reporting

The PI shall:

- Record every AE and observed PC, together with an assessment,
- Report to Baxter or designee, within 24 hours, all SAEs and PCs that could have led to a serious adverse device effect (SADE),
- Report to the IRB SAEs and PCs that could have led to a SADE if required by the national regulations or by the IRB,
- Supply Baxter or designee, upon Baxter's or designee's request, with any additional information related to the safety reporting of a particular event,
- Report any SAE if becoming aware after study completion of an SAE or PCs that could have led to a SADE that occurred in a patient during their participation in the study, the SAE must be reported on the SAE Form within 24 hours after awareness.

Baxter or designee shall report to regulatory authorities, SAEs and PCs that could have led to a SADE, as required by the national regulations.

7.2.1.1 Anticipated Adverse Events Related to Theranova and Hemodialysis

Anticipated Adverse Events related to the device or therapy can be found in the Investigator's Brochure (IB), investigational plan or application (including a supplementary plan or application).

7.2.2 Product Complaints/Product Issues

Any product complaints identified by the investigator or designee will be recorded in the PCs form and forwarded to Baxter within 5 days of becoming aware.

7.3 Medical Monitor

The medical monitor will regularly review data collected from eCRFs for potential safety concerns. A formal review plan of aggregate AEs/SAEs and PCs will be documented in a study Safety Management Plan.

Periodic review of reported AEs will be completed by Baxter or designee. At the site level the Investigator must assess risk and clinical significance of events to each individual study patient, including removing the patient from the study if necessary.

7.4 Safety Reporting to Authorities and IRB

It is the responsibility of the Investigator to report any SAEs to IRB according to local regulatory requirements.

Baxter or designee will assess each SAE reported by the Investigator to determine if the event qualifies as an Expedited Report according to local regulations. Expedited safety reports and associated Investigator letters will be submitted to the appropriate Authority and the Principal Investigator by Baxter or designee. The Investigator will file this Investigator letter and Expedited Safety Report in their study file. Additionally, a copy of the Safety Report and Investigator Letter will need to be submitted by the Investigator to their IRB, as appropriate per local regulations.

8. STUDY ACTIVITIES

8.1 Schedule of Evaluations and Procedures

All clinical study evaluations will be performed according to [Appendix 1](#) and the instructions listed below. If a patient discontinues from the study prematurely, every attempt will be made to perform all of the procedures and evaluations that are scheduled for the final visit (i.e. end of study visit).

8.2 Training for Theranova 400 dialyzer

Study personnel performing treatments with the Theranova 400 dialyzer for this clinical study will be comprised of physicians, HD nurses and other clinicians. Study staff will be trained on the use of the Theranova 400 dialyzer by the Sponsor's representative prior to patient enrolment. Training dates and training material will be documented and filled in the Investigator Site File per GDP.

8.3 Training for Elisio-17H dialyzer

Training will be provided on Elisio-17H dialyzers as applicable.

8.4 Screening Period (Days -14 to -1)

Prior to performing any study procedures, an IRB approved ICF must be signed and dated by each study patient and the person who administered the ICF. Prior to participation in the trial, the patient will receive a copy of the signed/dated ICF. The original signed/dated ICF must be retained at the site and confirmation of informed consent documented in the patient's medical record. All IRB approved revisions to the ICFs must be signed/dated by all patients who are currently enrolled in the study. The patient will receive a copy of the signed/dated revised ICF. Patients will be instructed to sign, or initial the consent form using their legal names (not nicknames).

Signing of the ICF and the initial Screening visit may occur on the same day, if necessary.

8.4.1 Assessments and Procedures

After providing written informed consent, patients will enter the Screening period. The aim of the Screening period is to assess the eligibility of patients for randomization and participation in the study. The maximum duration of the Screening period is 2 weeks. Screening period of 2 weeks was designed to provide adequate time to obtain screening lab results and complete all screening procedures. This period may not be used to repeat tests if initial tests result in study exclusion.

A complete medical history will include a review for all major body systems and renal history (primary etiology of renal disease, and current HD prescription). Medical history will also include an assessment of all medications being taken at the time of Screening, and any ESA taken in the 30 days prior to Screening, with each medication having a corresponding indication recorded on the concomitant medication eCRF form. Treatment parameters as described in Section 8.5.1 will be collected during treatment visits.

Further assessments include:

- Demographics
- Physical examination
- Vital signs
- Pregnancy test for women with child bearing potential
- AEs/SAEs

- Clinical laboratory evaluation as outlined in [Appendix 2](#)
- Randomization

8.5 Treatment Period (Day 1 to Day 168)

Study treatment period will consist of 3 weekly in-center treatments over a period of 24 weeks, where patients will receive HD treatment with either the Theranova 400 dialyzer or Elisio-17H dialyzer.

Please refer to [Appendix 1](#) for details of the Treatment Period activities and samplings.

8.5.1 Visit Procedures

Clinical laboratory evaluations will be taken at the first study dialyzer treatment and after every 4 weeks of treatment (i.e., Day 1 [first day of treatment], Week 4, Week 8, Week 12, Week 16, Week 20 and Week 24).

On the day of the study visit, the following dialysis treatment data will be collected:

- Treatment parameters:
 - Programmed Q_B , Q_D and ultrafiltration flow rate (Q_{UF}); (all in mL/min)
 - Actual Total Ultrafiltration volume at end of treatment (mL/Session)
 - Q_B will be documented at the start, every 30 minutes, and at the end of every study treatment
 - Total dialysis time
- Duration of and reasons for any treatment interruptions
- Concomitant medications
- AEs/SAEs/ADEs/PCs
- PRO measurements (KDQOL-36 and EQ-5D-5L)
- Vital signs
- Pre- and post-dialysis body weight
- Clinical laboratory evaluation as outlined in [Appendix 2](#)

8.6 End of Study Visitor Early Termination Procedures

The following information will be collected and procedures or evaluations will be performed during the End of Study visit (first non-study treatment, Week 25) or Early Termination.

- Physical examination including weight
- Vital signs
- AEs/SAEs/ADEs/PCs
- Concomitant medications
- Clinical laboratory evaluation as outlined in [Appendix 2](#)

If a patient discontinues from the study prematurely, every attempt should be made to perform all of the procedures and evaluations that are scheduled for the End of Study visit.

9. DATA MANAGEMENT, QUALITY CONTROL AND QUALITY ASSURANCE

The Sponsor is responsible for implementing and maintaining quality assurance and quality control systems with written SOPs to ensure that studies are conducted and that the data are generated, documented and reported in compliance with the protocol and applicable regulatory requirements. Quality control will be applied to all stages of data handling to ensure reliability and correct processing. The Sponsor is responsible for securing agreement from all involved parties to ensure direct access to all study related centers, source documents and reports for the purpose of monitoring and auditing.

Agreements made with the Investigator/institution will be in writing.

9.1 Auditing

The sponsor and/or sponsor's representatives may conduct audits to evaluate study conduct and compliance with the protocol, standard operating procedures, other written instructions/agreements, International Conference on Harmonization (ICH) GCP, the IRB and applicable regulatory guidelines/requirements. The investigator will permit auditors to visit the study site, as described in the Clinical Study Agreement. Auditing processes specific to the study will be described in the auditing plan.

10. PLANNED STATISTICAL METHODS

10.1 General Considerations

Further details of the planned statistical methods will be provided in the study statistical analysis plan (SAP). The purpose of the SAP is to further elaborate the statistical methods described in the protocol and describes analysis conventions to guide the statistical programming work. The SAP will be finalized at least two months prior to database lock. Any further clarification to the statistical methods described in the protocol will be documented in the SAP.

Unless otherwise noted, all analyses will be performed using SAS/GRAPH® 9.4 software, SAS/STAT® 14.1 software and Base SAS® 9.4. Copyright© 2002-2012, SAS Institute Inc. SAS and all other SAS Institute Inc. product or service names are registered trademarks or trademarks of SAS Institute Inc., Cary, NC, USA. All Rights Reserved.

Differences between treatment groups will be evaluated at a two-sided significance level of 0.050 (when rounded to 3 decimal places) and p-values < 0.050 will be considered statistically significant, unless otherwise noted.

Baseline measure for laboratory assessments is defined as the last non missing value obtained prior to dialysis on the day of the first study treatment. The final measure for laboratory assessments is defined as the last non missing value obtained after the day of the first study treatment.

10.2 Determination of Sample Size

The sample size for this study is driven by the primary safety endpoint. The sample size calculation was performed using PASS® 15.0.1 software, procedure Non-Inferiority Tests for the difference between Two Means. Copyright© 2017, NCSS, LLC. All Rights Reserved. The power is based on a t-test with a one-sided alpha level of 0.025 where the true difference in means is assumed to be zero (0) and the non-inferiority margin is 5%.

Pre-dialysis serum albumin was not evaluated in the previous Theranova 400 dialyzer HD study, only the mass (G) of albumin in the dialysate was assessed. However, a study published in PLoS ONE²⁶ did use a prototype of the Theranova dialyzer (MCO-CI) where in pre-dialysis albumin levels were collected after a month of therapy and, based on these data, a mean and standard deviation (SD) of 35.3 and 3.7 was observed.

Comparable pre-dialysis albumin levels are expected with both study dialyzers and with a sample size of 70 patients per group, a t-test with a 0.025 one-sided significance level will have 80% power to demonstrate non-inferiority of the Theranova 400 dialyzer compared to the Elisio-17H dialyzer as assessed by pre-dialysis serum albumin with a non-inferiority margin of 5%. To allow for 15% of patients to drop out, a total of 166 patients will be randomized 1:1 to treatment with the Theranova 400 dialyzer or treatment with the Elisio-17H dialyzer (i.e., 83 patients per group).

The 5% non-inferiority margin is based on results from 2 observational studies.^{27,28} These studies looked at the association between serum albumin levels and mortality in large US cohorts of HD and PD patients, respectively. In both studies, variations in serum albumin of +/- 1 g/L over 6 months (corresponds to +/-0.1 g/dL) have been defined as “stable serum albumin levels”. A variation of +/- 1 g/L is a range with a width of 2 g/L, which is

larger than 5% if applied to the reported mean baseline serum albumin levels. Therefore, a 5% variation in serum albumin can be justified as having no clinical significance.

A previously conducted Theranova 400 dialyzer prototype HDF study (Comparison of the Clinical Performance of Two Theranova 400 Dialyzer Prototypes in Hemodialysis Mode with the Performance of a High-Flux Dialyzer in Hemodialysis Mode and a High-Flux Dialyzer in High-volume Hemodiafiltration Mode – A Pilot Study, registered at clinicaltrials.gov, NCT02377622) was used to obtain λ FLC reduction ratio mean and standard deviation (SD) of 37.8 and 8.26. With a total sample size of 140 evaluable subjects as determined based on the primary safety endpoint (70 in the Theranova 400 dialyzer treatment group and 70 in the Elisio-17H dialyzer treatment group), a difference of 4.56 in the λ FLC reduction ratio in favor of the Theranova 400 dialyzer can be detected with 90% power at a two-sided 0.05 significance level using a two-sided two-sample t-test assuming equal variances. The sample size calculation for the primary efficacy endpoint was performed using PASS® 15.0.1 software, procedure Two-Sample T-Test Assuming Equal Variance.

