10.5.1 Primary Safety Endpoint(s)

For the primary safety endpoint of pre-dialysis serum albumin after 24 weeks of treatment, let μ_T denote the Theranova dialyzer pre-dialysis serum albumin mean and let μ_R denote the Elisio-17H dialyzer pre-dialysis serum albumin mean. Then the null hypothesis to demonstrate non-inferiority using a 5% margin can be expressed as:

$H_0: \mu_T - \mu_R \leq -1.765$. The alternative hypothesis is expressed as $H_a: \mu_T - \mu_R > -1.765$.

An ANCOVA model with fixed effects of treatment and site and the continuous fixed covariate of baseline pre-dialysis serum albumin will be used to generate a two-sided 95% confidence interval (CI) for the difference in treatment means ($\mu_T - \mu_R$). If the lower bound is > -1.765 then non-inferiority will be demonstrated.

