10.5.2 Primary Efficacy Endpoint(s)

For the primary efficacy endpoint of RR of λ FLC after 24 weeks of treatment, let μ_T denote the Theranova dialyzer RR of λ FLC mean at 24 weeks and let μ_R denote the Elisio-17H dialyzer RR of λ FLC mean at 24 weeks. Then the null hypothesis to demonstrate superiority can be expressed as:

$H_0: \mu_T - \mu_R = 0$. The alternative hypothesis is expressed as $H_a: \mu_T - \mu_R \neq 0$.

The primary safety analysis will be conducted first. If the primary safety analysis demonstrates non-inferiority, an ANCOVA model with fixed effects of treatment and site will be used to generate a two-sided 95% CI for the difference in treatment means ($\mu_T - \mu_R$). If the lower bound is > 0 then superiority will be demonstrated. The statistical testing of the primary efficacy endpoint of the reduction ratio (RR) of λ FLC after 24 weeks of treatment is contingent upon the outcome of the analysis of the primary safety endpoint and will only be conducted once non-inferiority could be established for the primary safety endpoint. This hierarchical testing approach guarantees that the overall type 1 error is controlled at a two-sided 0.05 significance level.

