5.3 Sample Size

The sample size for this study is driven by the primary safety endpoint. The sample size calculation was performed using PASS® 15.0.1 software, procedure Non-Inferiority Tests for the difference between Two Means. Copyright© 2017, NCSS, LLC. All Rights Reserved. The power is based on a t-test with a one-sided alpha level of 0.025 where the true difference in means is assumed to be zero (0) and the non-inferiority margin is 5%.

Pre-dialysis serum albumin was not evaluated in the previous Theranova 400 dialyzer HD study, only the mass (G) of albumin in the dialysate was assessed. However, a study published in PLoS ONE⁶ did use a prototype of the Theranova dialyzer (MCO-CI) where in pre-dialysis albumin levels were collected after a month of therapy and, based on these data, a mean and standard deviation (SD) of 35.3 and 3.7 was observed. Comparable pre-dialysis albumin levels are expected with both study dialyzers and with a sample size of 70 patients per group, a t-test with a 0.025 one-sided significance level will have 80% power to demonstrate non-inferiority of the Theranova 400 dialyzer compared to the Elisio-17H dialyzer as assessed by pre-dialysis serum albumin with a non-inferiority margin of 5%. To allow for 15% of patients to drop out, a total of 166 patients will be randomized 1:1 to treatment with the Theranova 400 dialyzer or treatment with the Elisio-17H dialyzer (i.e., 83 patients per group).

A previously conducted Theranova 400 dialyzer prototype HDF study (Comparison of the Clinical Performance of Two Theranova 400 Dialyzer Prototypes in Hemodialysis Mode with the Performance of a High-Flux Dialyzer in Hemodialysis Mode and a High-Flux Dialyzer in High-volume Hemodiafiltration Mode – A Pilot Study, registered at clinicaltrials.gov, NCT02377622) was used to obtain λ FLC reduction ratio mean and standard deviation (SD) of 37.8 and 8.26. With a total sample size of 140 evaluable subjects as determined based on the primary safety endpoint (70 in the Theranova 400 dialyzer treatment group and 70 in the Elisio-17H dialyzer treatment group), a difference of 4.56 in the λ FLC reduction ratio in favor of the Theranova 400 dialyzer can be detected with 90% power at a two-sided 0.05 significance level using a two-sided two-sample t-test assuming equal variances. Including 15% drop out, a total sample size of 166 (83 per treatment group) need to be enrolled into this study.

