12. EFFICACY PARAMETERS

Hypothesis testing of the primary efficacy endpoint will only be conducted if noninferiority could be established for the primary safety endpoint. The analysis of the primary efficacy endpoint will be carried out on both the FAS and PPS. The analysis using the PPS will be used as a supportive analysis.

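### The 90% power quoted for the λ FLC endpoint is stand-alone power; because that test runs only after albumin non-inferiority is shown, the power for the efficacy claim is 70% to 80% on the plan's own inputs

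*Protocol*

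**What the plan says.** The sample size is set by the primary safety endpoint. Protocol 10.2 states that "with a sample size of 70 patients per group, a t-test with a 0.025 one-sided significance level will have 80% power to demonstrate non-inferiority". The inputs are an external albumin result in which "a mean and standard deviation (SD) of 35.3 and 3.7 was observed", a true difference of zero and a 5% margin. Protocol 10.5.1 puts the margin in absolute terms: "If the lower bound is > -1.765 then non-inferiority will be demonstrated".

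The resulting 140 evaluable patients are then used for the efficacy endpoint. With an SD of 8.26, a λ FLC difference of 4.56 "can be detected with 90% power at a two-sided 0.05 significance level using a two-sided two-sample t-test". SAP 5.3 repeats that it "can be detected with 90% power at a two-sided 0.05 significance level", and the synopsis carries the same statement.

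The two primary endpoints are tested in a fixed order. Protocol 10.5.2 says that the efficacy test "will only be conducted once non-inferiority could be established for the primary safety endpoint". SAP 12 agrees: "Hypothesis testing of the primary efficacy endpoint will only be conducted if noninferiority could be established for the primary safety endpoint". Both documents discuss this ordering only as control of type I error.

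**The concern.** The 90% describes a test that is always carried out. In this design the test may not be carried out at all: if albumin non-inferiority fails, no superiority claim is possible however large the λ FLC difference. The power for the claim is therefore the probability of passing both tests, and on one set of planning inputs it cannot exceed the power of the first.

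Protocol 3.3 says that the trial's data are meant to support a new device classification based on removal of middle molecules such as λ FLC. The chance of obtaining that claim is a basic design figure, and the plan supplies only its more favourable component. The 80% target used for the blinded sample size reassessment (Protocol 10.8, SAP 7.3) does not fill the gap. It is driven by the albumin SD alone and so concerns the non-inferiority test.

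**Working it through.** **Inputs.** From Protocol 10.2, 10.5.1 and 10.5.2: 70 evaluable per group; albumin SD 3.7; margin 0.05 × 35.3 = 1.765; true albumin difference 0; one-sided α 0.025; λ FLC SD 8.26; difference 4.56; two-sided α 0.05. The documents give no correlation between the two endpoints.

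**Formula.** For each two-sample t-test, SE = SD × √(2/n). Power is the probability that a non-central t variable with 138 df and non-centrality (distance / SE) exceeds the critical value 1.977.

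**Step 1: reproduce the plan's figures.**

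| Test | SE | Non-centrality | Power |
|---|---|---|---|
| Albumin non-inferiority | 3.7 × √(2/70) = 0.6254 | 1.765 / 0.6254 = 2.822 | 0.800 |
| λ FLC superiority | 8.26 × √(2/70) = 1.396 | 4.56 / 1.396 = 3.266 | 0.900 |

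The difference detectable at exactly 90% power is 4.558, against 4.56 stated. Both stated powers are right as stand-alone figures.

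**Step 2: power to pass both tests.**
- Independent tests: 0.8002 × 0.9003 = 0.720.
- Lowest possible under any dependence: 0.8002 + 0.9003 − 1 = 0.701.
- Highest possible under any dependence: min(0.8002, 0.9003) = 0.800.
- Bivariate normal test statistics:

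| Correlation of the test statistics | −0.5 | −0.3 | 0 | 0.3 | 0.5 | 0.9 |
|---|---|---|---|---|---|---|
| Power to pass both | 70.3% | 70.8% | 72.0% | 73.8% | 75.2% | 79.2% |

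**Step 3: is 90% a conditional power?** Conditional power is the power to pass both divided by the non-inferiority power. At correlation −0.5 it is 0.703 / 0.800 = 0.88; at 0 it is 0.90; at 0.5 it is 0.752 / 0.800 = 0.94. The 90% equals the conditional power only if the tests are independent.

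**Step 4: planned albumin analysis.** The primary albumin model is an ANCOVA with baseline albumin. If r is the correlation of baseline with week-24 albumin (assumed; not in the documents), the effective SD is 3.7 × √(1 − r²). With no albumin deficit and independent tests:

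| Assumed r | Effective SD | Non-inferiority power | Power to pass both |
|---|---|---|---|
| 0.5 | 3.20 | 0.899 | 0.899 × 0.900 = 0.81 |
| 0.7 | 2.64 | 0.975 | 0.975 × 0.900 = 0.88 |

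**Step 5: a small true albumin deficit.** Protocol 1.2 acknowledges greater albumin removal per treatment with the test device than with high-flux dialyzers. If the true deficit were 0.25 or 0.5 g/L (assumed values, inside the margin), unadjusted non-inferiority power would be 0.672 or 0.519. The power to pass both would then be 0.61 or 0.47, with independent tests. At r = 0.7 and a deficit of 0.5 g/L it would be 0.803 × 0.900 = 0.72.

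**The case against.** The strongest reply is that nothing has been miscalculated. Protocol 10.2 names the test, the number of patients, the SD, the difference and the software procedure, and on those inputs 90% is right. Both powers and the testing order are disclosed, and no passage calls 90% the overall chance of an efficacy claim. All of that stands. A reader might infer an arithmetic error; there is none. What is missing is a label on the 90% and the power to pass both tests.

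Second, 4.56 is the difference that a sample fixed by the safety endpoint can detect; it is not put forward as the expected effect. That is fair, so 72% is not a forecast of the trial's success. A larger effect helps only up to the limit set by the first test: on the t-test basis with independent tests, differences of 6 and 8 points give 79.2% and 80.0%.

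Third, a reader might infer that 80% is a hard ceiling for the trial as it will be analysed. The documents do not support that. The ceiling belongs to the unadjusted t-test at 70 per group with SD 3.7, and the baseline-adjusted model can exceed it, as shown above. A smaller SD would also raise it, because the reassessment never reduces the sample: at 70 per group, non-inferiority power is 0.86 at SD 3.4 and 0.90 at SD 3.2. If all 83 randomized per group contributed full information, the product would be 0.863 × 0.942 = 0.81. These are reasons to show the planning figure with its assumptions, but none of them makes 90% the power for the efficacy claim on the stated inputs.

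**Conclusion.** The point holds as misreported design power. The 90% is the correct stand-alone power of the λ FLC t-test. With the required non-inferiority step, the power for the efficacy claim on the plan's own t-test inputs is 72% if the tests are independent and 70% to 80% under any dependence, which is 10 to 20 percentage points below the figure shown. Independence is an assumption made here and appears in neither document, so the range should accompany the 72%.

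Two further readings should be avoided. Relabelling the 90% as power given that non-inferiority has been shown would be wrong unless the tests are independent. Treating 72% as the power of the planned ANCOVA would also be wrong: at r = 0.5 to 0.7 (assumed), no albumin deficit and independent tests, that figure is about 81% to 88%. Type I error control is not affected.

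**What to change.** In the synopsis, Protocol 10.2 and SAP 5.3:

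1. Label the 90% as the stand-alone power of the superiority t-test, before account is taken of the non-inferiority requirement. Do not call it conditional power.
2. Add the power to pass both primary tests: 72% if independent, range 70% to 80%, on the t-test basis with 70 per group, SD 3.7, margin 1.765, no true albumin difference and a 4.56-point λ FLC difference.
3. Beside it, give a figure for the planned baseline-adjusted albumin ANCOVA with its assumed correlation stated: about 81% at r = 0.5 and 88% at r = 0.7, with no albumin deficit and independent tests.

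The sample size, type I error control, analyses and decision rules stay as they are. The only cost is a less favourable stated figure.
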